NCT04805515

Impact of Nicotine Messaging on Nicotine Beliefs and Tobacco Use Behavior

Document date: December 18, 2020

Contents

Study Protocol.....	2
Study Measures	3
Statistical Analysis Plan	4
References	6

Study Protocol

The current study tests the impact of multiple exposures to a brief nicotine corrective messaging intervention on beliefs about nicotine and on intention and use of tobacco and nicotine products in a 12-week population-based study of 794 adult smokers and non-smokers who are registered Amerispeak national consumer market research panel members. Data were collected by National Opinion Research Center (NORC) at the University of Chicago and sent de-identified to the PI and study team. A parallel lab-based study will be conducted in adult smokers followed for 4 weeks (NCT05108649) who also receive normal nicotine content or reduced nicotine content cigarettes and are explicitly told which product they have been given (i.e., unblinded).

For the population-based study, AmeriSpeak panel members received a standard email invitation describing the study. NORC obtains and documents participants' informed consent at the time of registration in the Amerispeak panel. Potential participants are identified by randomly selecting households within the panel with an adult within the study age range, and targeting study invitations based on recent study participation, and other demographic characteristics as needed to ensure a representative sample. This email invitation introduced study procedures and eligibility criteria, and directed interested panel members to the eligibility screener with items to confirm eligibility. Procedures ensured that potential participants are adults ages 18 and older through two steps: 1) targeting study invitations only to those panel members whose age was within this range; and 2) re-assessing age at eligibility screening and excluding those who provide inconsistent information. Panel members who were confirmed to meet study eligibility criteria proceeded to the online experiment. AmeriSpeak panel members who did not meet study eligibility criteria were redirected to a concluding thank-you screen.

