Perceived message effectiveness	Wave 4	Week 5
Message credibility	Wave 4	Week 5
Eye-tracking		Weeks 1-4
Biomarkers		Weeks 0, 5
Outcomes		
Nicotine beliefs	Waves 1, 2, 4	Weeks 0, 2, 5
Intention to use nicotine/tobacco products	Waves 1, 2, 4	Weeks 0, 2, 5
Nicotine/tobacco use and behavior	Waves 1, 2, 4	Weeks 0, 2, 5
Subjective rating of study cigarette		Weeks 1-5
Manipulation check	Waves 1, 2, 4	Weeks 0, 2, 5
Moderators		
Sociodemographics	Wave 1	Week 0
Literacy	Wave 1	Week 0
Cancer risk beliefs	Wave 1	Week 0
Cancer risk behaviors	Wave 1	Week 0
Fagerstrom test for nicotine dependence	Wave 1	Week 0
Other key constructs		
Attitudes about nicotine	Waves 1, 2, 4	Weeks 0, 2, 5
Nicotine-related norms	Waves 1, 2, 4	Weeks 0, 2, 5
Behavioral control	Waves 1, 2, 4	Weeks 0, 2, 5
Stages of change	Wave 1, 4	Week 0, 5
Policy support	Wave 4	Week 5

Statistical Analysis Plan

Sample Size. Power for Aim 1 was calculated for 715 adults with 70% retention at 12-weeks follow-up. Our pilot data provide estimates of the magnitude of the effect of the Nicotine Corrective Messaging (NCM) intervention on the primary outcome of nicotine beliefs, including four continuous scales on nicotine false beliefs, NRT false beliefs, e-cigarette false beliefs, and reduced nicotine content (RNC) cigarette false beliefs.¹ With an expected final sample size of 500 and ignoring repeated measures, we will have 80% power to detect differences of <1 unit between the intervention and control group means for the nicotine, NRT, and e-cigarette false belief scales and a 1.64 difference in the group means for the RNC cigarette false beliefs scale. These equate to small-to-medium effect sizes (Cohen's *d* ranging from 0.25 to 0.27), which are smaller than the effects observed for nicotine and NRT false beliefs outcomes in the pilot study.¹

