Exploratory analyses will focus on three areas: 1) potential moderators of the relationship between intervention condition and the study outcomes; 2) nicotine beliefs as a potential mediator of the relationship between intervention condition and constructs identified in the Theory of Planned Behavior (i.e., nicotine-related attitudes, norms, behavioral control, and nicotine/tobacco intentions and use); and 3) the relationship between visual attention to nicotine education messages and nicotine beliefs in the participants exposed to the NCM intervention.

For the first area (*moderation*), we will conduct exploratory analyses using the same steps described for Hypothesis 1b to determine whether there are potential moderators of the relationship between the intervention(s) and outcomes, specifically age, gender, literacy, baseline cancer beliefs and cancer risk behaviors.

For the second area (*mediation*), we will draw from traditional mediation frameworks and use robust methods to explore the relationships outlined in our theoretical framework, specifically whether changes in nicotine beliefs post-exposure (Wave 2) influence nicotine-related attitudes, norms, behavioral control, intention, and behavior at the final assessment (Wave 4). We will examine whether nicotine beliefs at Wave 2 are associated with these outcomes using bivariate statistics and regression-based analysis accounting for any covariates as described above. Where these preliminary steps indicate potential correlation between nicotine beliefs and study outcomes ($p < .05$), we will test for mediation by estimating the indirect effects of nicotine beliefs on follow-up outcomes via the intervention condition using a bias-corrected bootstrapping method with 1,000 resamples. This approach estimates indirect (i.e., mediation) effects and produces bias-corrected asymmetric 95% CIs correcting for non-normality of the distribution of indirect effects and providing higher power and better control over the Type I error rate versus traditional approaches to test mediation. Asymmetric 95% confidence intervals around indirect effect estimates for nicotine beliefs that do not include zero will be interpreted to indicate significant mediation.

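### The SAP credits its mediation test with better Type I error control, but the bias-corrected bootstrap interval can exceed 5% (about 6% to 7.5%) when the messaging does not move a belief that predicts the outcome

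*Combined protocol and SAP*

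**What the plan says.** The Analytic Approach section of the Statistical Analysis Plan states that "Exploratory analyses will focus on three areas"; mediation is the second. Wave 2 nicotine beliefs are first related to the Wave 4 Theory of Planned Behavior outcomes. "Where these preliminary steps indicate potential correlation between nicotine beliefs and study outcomes" at p < .05, the indirect effect is estimated "using a bias-corrected bootstrapping method with 1,000 resamples".

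The decision rule is: "Asymmetric 95% confidence intervals around indirect effect estimates for nicotine beliefs that do not include zero will be interpreted to indicate significant mediation". The method is recommended as "providing higher power and better control over the Type I error rate versus traditional approaches to test mediation". That sentence gives no error rate, cites no source and names no comparator.

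On size, the Sample Size paragraph says: "Power for Aim 1 was calculated for 715 adults with 70% retention at 12-weeks follow-up", and then "With an expected final sample size of 500 and ignoring repeated measures, we will have 80% power". The opening of the Study Protocol describes a "12-week population-based study of 794 adult smokers and non-smokers".

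**The concern.** An indirect effect is the product of two paths: condition to belief (a) and belief to outcome (b). It is zero if either path is zero. When one path is zero and the other is moderate, the bootstrap distribution of the product is skewed away from zero. The bias correction responds by moving both limits further from zero, so the interval clears zero more often than its nominal level allows.

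The case that matters here is a = 0 with b not zero: NCM leaves a belief scale unchanged, but people who hold the belief differ in attitudes or intentions. This is plausible for some of the four scales. The Sample Size paragraph compares its detectable effects with pilot effects for the nicotine and NRT scales only, and says nothing comparable for the e-cigarette and RNC scales. At stake is a finding labelled significant mediation with a higher false-positive risk than the 95% interval implies, in a plan that presents error control as a strength of the method.

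**Working it through.** **Inputs from the documents.** Final N = 500; equal allocation; detectable d of 0.25 to 0.27; 1,000 resamples; 95% interval; p < .05 screen on the belief-outcome association. **Not in the documents:** the size of b, so a range was run; and the alpha for the sample size, taken as two-sided 5%.

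**1. The plan's own figure.** The SAP states no Type I error figure for mediation, so the sample size is what can be reproduced. Detectable d = (1.960 + 0.842) × √(2/250) = 0.2506, and power at d = 0.25 is 79.8%. This matches the lower end, 0.25. (At d = 0.27 the same formula gives 85.5%, so the upper end does not follow from it; nothing here depends on that.) Enrolment: 500/0.70 = 714.3, rounded up to 715. At 70% retention, 794 gives 556.

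**2. The two intervals.** Let z0 = Φ⁻¹(share of bootstrap products below the estimate). The bias-corrected limits are the bootstrap quantiles at Φ(2·z0 ± 1.96). The percentile limits set z0 = 0.

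**3. False-positive rates at N = 500.** Linear model, normal errors with residual SD 1, no direct effect, 1,000 resamples, 12,000 simulated trials (Monte Carlo SE about 0.2 points). The z of the non-zero path is b√500 or a√500/2. Entries are percentages of all trials. BC is bias-corrected; the last column counts trials that pass the bivariate screen and also reject.

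| a | b | z | BC | Percentile | Joint | Sobel | Causal steps | Screen and BC |
|---|---|---|---|---|---|---|---|---|
| 0 | 0 | - | 0.48 | 0.12 | 0.22 | 0.00 | 0.02 | 0.34 |
| 0 | 0.10 | 2.2 | 5.17 | 2.36 | 2.94 | 0.48 | 0.15 | 4.72 |
| 0 | 0.14 | 3.1 | 6.90 | 3.93 | 4.15 | 1.28 | 0.18 | 6.71 |
| 0 | 0.20 | 4.5 | 7.13 | 4.89 | 4.64 | 2.60 | 0.35 | 7.11 |
| 0 | 0.30 | 6.7 | 6.17 | 5.00 | 4.66 | 3.80 | 0.40 | 6.17 |
| 0 | 0.39 | 8.7 | 5.64 | 5.00 | 4.66 | 4.21 | 0.44 | 5.64 |
| 0.25 | 0 | 2.8 | 6.73 | 3.58 | 3.97 | 0.98 | 0.34 | 3.88 |
| 0.27 | 0 | 3.0 | 7.21 | 3.91 | 4.18 | 1.17 | 0.33 | 4.09 |
| 0.39 | 0 | 4.4 | 7.32 | 5.08 | 4.84 | 2.50 | 0.39 | 4.29 |

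In every null scenario run, BC rejects more often than each of the other four methods.

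**4. Second method.** A normal-theory simulation (20,000 trials per point, 1,000 draws per interval, a = 0, belief-outcome z from 2.8 to 8) gives BC 6.0% to 7.5%, percentile 3.5% to 5.3% and joint significance 4.0% to 5.3%.

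**5. The screen when a = 0.** The screen selects on b, so it does not guard against a null a. Among tests that pass it, the BC rate is (screen and BC)/(screen passed): 6.71/87.72 = 7.6% at b = 0.14, and 7.11/99.31 = 7.2% at b = 0.20. The normal-theory runs give 6.0% to 7.9% over z of 2.8 to 8.

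**6. The screen when b = 0.** Here the screen tests the null path itself and is passed in only about 5% of trials. The whole procedure therefore rejects in 3.9% to 4.3% of all trials in the last three rows, and 3.5% to 3.8% if the covariate-adjusted association must also be significant. The normal-theory figure is 4.3% to 4.8%. All are below 5%.

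**7. Number of resamples and sample size.** With 20,000 draws per interval, BC is still 6.6%, 7.6%, 7.0%, 6.2% and 5.8% at z = 2.8, 3.5, 4.5, 6 and 8, so more resamples do not cure it. The peak is 7.4% at N = 556 and 7.7% at N = 794 (4,000 trials each, SE about 0.4 points).

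**8. Power given up.** With the a-path at the design effect (z = 2.8), moving from BC to percentile lowers power from 56% to 45% at b z = 2.2, from 72% to 62% at 2.8, and from 80% to 73% at 3.5. Across the runs the loss is about 4 to 12 points, or 4 to 7 with the screen.

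**The case against.** The strongest reply concerns the comparator. The SAP claims an advantage over traditional approaches, most naturally the Sobel and causal-steps tests. These are very conservative. If control means closeness to 5%, BC is nearer than Sobel: at b = 0.14 it misses by 6.90 − 5 = 1.90 points against 5 − 1.28 = 3.72, and at b = 0.20 by 2.13 against 2.40. At b = 0.10, BC (5.17%) is also nearer to 5% than the percentile interval (2.36%). This stands in part: the clause is ambiguous, and a reader might infer that it is false on every reading, which goes too far. But in the usual sense of not exceeding the nominal level, BC does worse than Sobel and causal steps. On the closeness reading it still loses to the percentile interval and joint significance where it peaks (at b = 0.20, misses of 0.11 and 0.36 points).

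The second reply is that the screen already deals with a null belief-outcome path. That stands. At the design effect of 0.25 to 0.27 with b = 0, the screened procedure stays below 5%. Only the a = 0 case keeps the excess.

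The third reply is that the analysis is exploratory, that the SAP's claim of higher power is not contradicted, and that some power is lost by switching. All of this stands and limits the importance of the point. Part of the extra power, however, comes from the inflated error rate.

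**Conclusion.** The error-control justification is not supported. With no NCM effect on a belief and a belief-outcome z of about 2.8 to 8, the nominal 5% rule rejects about 6% to 7.5% of the time (about 6% to 8% among tests passing the screen), which is 1.2 to 1.5 times nominal (6/5 to 7.5/5), or up to 1.6 times after the screen (8/5). The percentile interval and joint significance hold about 5% or less in the same setting.

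A reader might infer that 7% to 8% is the general false-positive rate for mediation in this trial. The documents do not support that. They give no belief-outcome association, and the rate at N = 500 runs from about 0.5% to a peak of 7.3% over the null scenarios before screening. The excess falls back toward 5.5% when b is large.

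The figures assume linear models with normal errors, no covariates and no missing data. The binary intention and use outcomes were not simulated. The severity is minor.

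**What to change.** For the rule that declares significant mediation, use the 95% percentile bootstrap interval from the same resamples, or the joint-significance test. Delete the Type I error part of the justification. If it is kept, qualify it to say that the bias-corrected interval has higher power than Sobel or causal steps but can exceed the nominal level when one path is null. The bias-corrected interval can remain at most as a sensitivity analysis.

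The change costs one software option and one clause, plus the loss of mediation power shown in step 8. The SAP should acknowledge that loss and not describe it as negligible. The primary and secondary analyses need no change.

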Analyses for Aims 1 and 2 employ common measures and a common analytic framework to test the impact of nicotine education on nicotine beliefs and behavior. Primary analyses will use an intention-to-treat approach. We will conduct sensitivity analyses with different assumptions for the missing data mechanism including analyzing complete data only⁹ and last observation carried forward. Outcomes for Aim 1 focus on continuous measures (*primary outcome*: nicotine beliefs; *secondary outcomes*: frequency of nicotine/tobacco use), with the primary hypotheses (**Hypotheses 1a**) focused on the effect of the intervention on these outcomes. Preliminary analyses will examine differences in these outcomes across study conditions at the first post-exposure time point (Wave 2) and at the final timepoint (Wave 4) controlling for covariates that are differentially distributed between study groups. In Aim 1, we will also use multiple logistic regression models to examine effects of the NCM intervention on the proportion of participants reporting specific nicotine beliefs (i.e., "nicotine is a cause of cancer"), intentions to use cigarettes, e-cigarettes, NRT, and low nicotine cigarettes in the next 12 months, and

tobacco/nicotine use (e.g., any new use/trial, any past 30-day use, product-specific past 30-day use).

For **Hypothesis 1b**, we will evaluate whether current smoking moderates the effect of NCM on our primary and secondary outcomes by incorporating an interaction between study condition (NCM/control) and current smoking status (smoker/non-smoker) through the following steps: 1) bivariate analyses, to determine if outcomes vary by these variables; 2) testing whether current cigarette smoking moderates ($p < .05$) experimental effects in the models above by the addition of a study condition-by-smoking status interaction term into the model; 3) if no evidence of moderation exists, including cigarette smoking as a covariate.

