For the third area (*visual attention*), we will use data from the Wave 1 heatmapping task among participants in the NCM condition to identify regions of interest (ROIs) on each of the nicotine education messages and code these as ROIs across all Waves. We will explore whether attention to (i.e., clicking on) the ROIs is correlated with scores on the nicotine beliefs scales (i.e., nicotine, NRT, e-cigarette, RNC cigarette beliefs) at the same assessment (Wave 4). Given the content of messages in the nicotine education condition, we will be able to assess whether attention to specific ROIs is correlated with specific beliefs (i.e., whether clicking on a specific ROI within the “Nicotine does not cause cancer” is correlated with response to the nicotine belief item regarding nicotine causing cancer). We will also be able to explore the prospective relationship between visual attention to the nicotine education messages (e.g., duration spent viewing messages, attention to ROIs) and nicotine beliefs and whether there are differences in visual attention in the NCM intervention condition over the four waves of data collection. These data will inform potential refinements to nicotine education messages for future studies.

Missing data: The most effective approach to eliminating biases and inefficiency caused by missing data is to collect complete data. In both aims of our study, we will use several tools available to maintain contact and verify that forms are complete. Use of computerized survey platforms in this study will provide additional mechanisms to improve completeness of survey responses, but even so, some participants may refuse to answer certain questions. We anticipate that one cause of missing data will be item non-response on self-report questionnaires; another will be missing assessments. When practical, missing items will be imputed using conditional means, estimated with an iterated version of Buck's method.¹⁰ Another cause of missing data is attrition, and we will pursue a range of model-based analyses that account for dropouts assuming data are missing at random (MAR), including multiple imputation methods (MI).^{11,12} We will also conduct sensitivity analyses with different assumptions for the missing data mechanism including analyzing complete data only⁹ (missing completely at random, MCAR) and last observation carried forward, in which subjects without self-report follow-up data will be considered to have no change.

References

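### For new use/trial, the carry-forward sensitivity analysis fills in no event for anyone without a follow-up report, so it cannot test for excess uptake among dropouts

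*Combined protocol and SAP*

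**What the plan says.** The Missing data paragraph of the SAP handles attrition through "model-based analyses that account for dropouts assuming data are missing at random (MAR), including multiple imputation methods (MI"). It then adds: "We will also conduct sensitivity analyses with different assumptions for the missing data mechanism including analyzing complete data only", with, as the second such analysis, "last observation carried forward, in which subjects without self-report follow-up data will be considered to have no change". Analytic Approach names the same two sensitivity analyses. Neither place restricts carry-forward to the continuous outcomes.

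Analytic Approach also says that "we will also use multiple logistic regression models to examine effects of the NCM intervention" on several binary outcomes, among them "tobacco/nicotine use (e.g., any new use/trial, any past 30-day use, product-specific past 30-day use"). So new use/trial is analysed on the odds-ratio scale, and the carry-forward rule covers it as written. The plan does not say how the rule is coded for this outcome.

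Two other facts bear on the point. Use is measured at Waves 1, 2 and 4 (Study Measures), so some participants lost by Wave 4 will have a Wave 2 report. The Sample Size paragraph plans for substantial loss: "Power for Aim 1 was calculated for 715 adults with 70% retention at 12-weeks follow-up".

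**The concern.** Carrying a value forward needs an earlier value of the same quantity. A belief score has one at Wave 1. New use/trial does not: at baseline nobody can yet have had the event, so the only value that no change can supply is no. For a participant with no follow-up report, the rule assigns the answer instead of assuming something about a trajectory.

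The question a sensitivity analysis should answer here is whether a finding of no increase in new use would survive if the people who left had taken up products more often than those who stayed. An analysis that enters no event for all of them cannot answer it. Its agreement with the other analyses could still be read as evidence of robustness. A second risk is that, if retention differs between arms, the filled-in zeros fall unevenly and shift the comparison. That is conceivable under this design, because only NCM participants receive the Wave 3 survey and contact therefore differs by arm.

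**Working it through.** **Inputs from the plan.** 715 adults, equal allocation (357.5 per arm), 70% retention, logistic regression for binary outcomes.

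**Assumed inputs.** New-use rates and arm-specific retention, which the documents do not give. Except where stated under objection, dropouts are taken to have no Wave 2 report.

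**1. The plan's own figure.** 715 × 0.70 = 500.5, which matches the stated 500. With 250 per arm and a two-sided 5% level (assumed, as the paragraph states none), the smallest difference detectable with 80% power is (1.960 + 0.842) × √(2/250) = 0.2506 SD. That agrees with the lower end of the stated Cohen's d, "ranging from 0.25 to 0.27". It concerns the continuous belief scales and is unaffected by this point. It is used here only for the sample size and the 30% loss.

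**2. What the rule records.** With retention r and true rate p in an arm, recorded rate = r × p + (1 − r) × 0 = r × p.

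**3. Equal retention, 15% vs 10%.** Complete cases: 0.70 × 357.5 = 250.25 per arm. Carry-forward: 357.5 per arm, with recorded rates 0.70 × 15% = 10.5% and 0.70 × 10% = 7.0%.

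SE(log OR) = √[1/(n₁p₁(1−p₁)) + 1/(n₀p₀(1−p₀))]; SE(RD) = √[p₁(1−p₁)/n₁ + p₀(1−p₀)/n₀].

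| | Complete case | Carry-forward |
|---|---|---|
| Odds ratio | 1.59 | 1.56 |
| SE(log OR) | 0.275 | 0.270 |
| z for log OR | 0.463/0.275 = 1.68 | 0.444/0.270 = 1.65 |
| Risk difference (points) | 5.0 | 3.5 |
| SE(RD) (points) | 2.95 | 2.11 |
| z for RD | 1.70 | 1.66 |

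Rates and risk difference shrink by 30%. On the planned logistic scale almost nothing moves, so the analysis nearly repeats the complete-case result.

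**4. Dropouts who differ, NCM only.** Respondents have 10% new use in both arms and retention is 70%. NCM dropouts have three times the odds; control dropouts match respondents.

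- Odds among NCM dropouts: 3 × 0.10/0.90 = 0.333, so their rate is 0.333/1.333 = 25%.
- True NCM rate: 0.70 × 10% + 0.30 × 25% = 14.5%. True control rate: 10%.
- True odds ratio: (0.145/0.855)/(0.10/0.90) = 1.53.
- Complete case: 10% vs 10%, odds ratio 1.0.
- Carry-forward: 7% vs 7%, odds ratio 1.0.
- Missing-at-random imputation without predictors that explain the excess: about 10% vs 10%, odds ratio about 1.0.

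The same steps from other respondent rates give a true odds ratio of 1.56 at 5% (dropouts 13.6%, NCM overall 7.59%) and 1.47 at 20% (dropouts 42.9%, NCM overall 26.9%). Complete case and carry-forward give 1.0 each time, so the blindness does not depend on the rate chosen.

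**5. Unequal retention, no true effect.** With 10% in both arms and retention 75% and 65%, recorded rates are 7.5% and 6.5%. The odds ratio is (0.075/0.925)/(0.065/0.935) = 1.17, with z = 0.154/0.294 = 0.52. With a true 10% vs 5% (odds ratio 2.11), the recorded odds ratio is 2.41 if the arm with the higher rate has 75% retention (7.5% vs 3.25%), and 1.78 if it has 65% (6.5% vs 3.75%).

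**The case against.** The case against is substantial, and most of it stands as a limit on the point.

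- **Carry-forward is only a sensitivity analysis.** Attrition is otherwise handled by missing-at-random models with multiple imputation, and a complete-case analysis is also planned. No conclusion rests on carry-forward alone. This stands, but step 4 shows that none of the three need detect the departure that matters most.
- **The outcome is of low rank.** Nicotine beliefs are primary and frequency of use is secondary. New use/trial is one example among additional binary analyses. This stands and sets the severity.
- **Wave 2 reports.** A reader might infer that every participant lost to follow-up becomes a non-initiator. The documents do not support that. The rule addresses people without follow-up self-report, and use is measured at Wave 2, so a Wave 2 yes can be carried. The documents give no Wave 2 retention. If half of the dropouts' events were seen at Wave 2, a true 10% vs 5% would be recorded as 0.70 × 10% + 0.30 × 0.5 × 10% = 8.5% vs 4.25%, an odds ratio of 2.09 against 2.11. The remaining dropouts are still filled in as no.
- **False precision.** A reader might infer that the filled-in zeros produce a misleadingly small standard error. SE(RD) does fall by 28% in step 3 (2.95 to 2.11 points), but the difference falls with it and z barely changes. On the planned scale SE(log OR) falls by 2%.
- **Unequal retention is hypothetical.** 75% and 65% appear nowhere in the plan, and the artefact in step 5 is far from significance at this sample size. It shows direction and size and predicts nothing about this trial.

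**Conclusion.** The point holds as a minor one. As written, the carry-forward rule codes new use/trial as no for everyone without a follow-up report, and so cannot test whether dropouts had more new use than respondents. Under equal retention it adds almost nothing to the complete-case odds ratio (1.59 to 1.56). Under unequal retention it can create or distort a difference (1.00 to 1.17). It would miss a true odds ratio of 1.53 arising among NCM dropouts. All of these sizes rest on assumed rates and retention, and on dropouts having no Wave 2 report.

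Two stronger readings should be resisted. One is that the rule cannot be applied to this outcome at all. It can: it is a single extreme assumption that nobody without a report started, and the plan should label it so. The other is that carry-forward must also go for past 30-day use. That outcome has Wave 1 and Wave 2 values to carry. For a participant missing both follow-ups, pre-message behaviour does stand in for Wave 4 behaviour, but preferring another method there is a matter of judgement and does not follow from this argument.

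**What to change.** Add to the Missing data paragraph:

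- Carry-forward is not used as the sensitivity analysis for any new use/trial. It may stay for past 30-day use.
- New use/trial is defined over Waves 2 and 4, so that a Wave 2 report counts.
- Its missing values are handled by the multiple imputation already planned, run by arm with Wave 1 use and Wave 2 reports as predictors.
- For sensitivity, values are re-imputed with dropouts' odds of new use multiplied by, for example, 1, 2 and 3, first in both arms and then in NCM only.
- Treating all missing as no new use may be shown, but only as a labelled extreme.

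The cost is a few sentences in the SAP and one short extra analysis on imputations that will exist anyway. The sensitivity intervals will be wider than carry-forward would show. The multipliers are a judgement and should be fixed before the outcome data are examined by arm.
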